8.4. Examination of Subgroups

All efficacy variables will be summarized by number of prior HER2-directed regimens in the metastatic setting, geographic region, hormone receptor status, and disease category. These analyses will be presented using forest plots and tests of interaction will be done. PFS and OS will, in addition, be summarized by de novo MBC vs. recurrent MBC.

8.5. Exploratory Biomarker Analysis

Future exploratory biomarker evaluations may include but are not limited to quantitative measures of HER2, gene expression analysis, and genomic analysis including but not limited to PIK3CA mutation status. The role of the immune response including measurement of tumor infiltrating lymphocytes (TILS) and levels of immune markers may also be assessed.

9. SAFETY EVALUATION

9.1. Overview of Safety Analysis Methods

All safety analysis will be performed for all patients in the Safety population. The following assessments will be used to evaluate the safety of neratinib in combination with capecitabine in HER2+ metastatic breast cancer (MBC) patients whose disease has progressed following two (2) prior HER2+ directed regimens in the metastatic setting:

- Adverse events (AEs)
- Medical history
- Vital sign measurements
- Physical examination findings
- Electrocardiogram (EKG)
- LVEF results from multiple-gated acquisition scan (MUGA) or echocardiogram (ECHO)
- Liver Function Tests results
- Eastern Cooperative Oncology Group (ECOG) performance status
- Laboratory assessments

All safety endpoints will be summarized by treatment group and visit when appropriate.

9.2. Extent of Exposure

Extent of exposure to each investigational product will be summarized by total dose, number of cycles, number of missed doses, number of dose delays and number of dose reductions.

9.3. Adverse Events, Serious Adverse Events, and Deaths

All AEs and SAEs will be reported until 28 days after the last dose of investigational product(s) and will be followed until resolution or until condition stabilizes. Should an Investigator be made aware of any SAE occurring any time after the reporting period, it must be promptly reported. The Patient Diary used for recording of investigational product intake will also be used by patients to document any AEs experienced during study treatment. In the case of diarrhea, it also serves to document the number of loose stools per day and use of loperamide/other antidiarrheal treatments taken.

AEs and SAEs will be coded using the most current version of MedDRA and tabulated by system organ class (SOC) and preferred term (PT). All AEs will be graded by the Investigator according to the NCI CTCAE v.4.0. Summaries will in general focus on treatment emergent adverse events (TEAEs). A TEAE is any adverse event that occurs or worsens on or after first dose of investigational product and up to 28 days after the last dose.

TEAEs and SAEs will be tabulated by SOC, PT, and treatment group. All tabulations will be sorted by descending frequency of SOC and PT in the total column unless otherwise noted. TEAEs will also be summarized according to relationship to study drug and severity. TEAEs of toxicity grade 3 or higher will also be summarized.

Similarly, treatment emergent adverse events leading to treatment discontinuation, dose modification, dose hold, and/or delay of investigational product will be tabulated by SOC, PT and treatment group.

Separate summaries and comparisons between treatment groups will be presented for treatment emergent diarrhea events leading to treatment discontinuation, dose holds, dose reductions, and delay of investigational product. Therapies used to treat diarrhea will also be summarized using descriptive statistics and compared between treatment groups.

SAEs, and TEAEs will be listed in by patient listings sorted by treatment, patient ID and study day; SAEs will be flagged. All AE listings will include study day, SOC, PT, reported term, dose, Cycle/day, AE onset date, AE resolution date, outcome, duration, relationship to drug, action taken, and severity.

Patient deaths are recorded on the End of Study CRF page. The number and incidence of death will be summarized by cause of death overall, treatment arm, and on-study status at time of death (within 28 days of last dose vs. more than 28 days after last dose). Patient death listings will include all death data available including date of death, cause of death and any AEs resulting in death.

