7.1 Required Concomitant Treatment

7.1.1 Loperamide Antidiarrheal Therapy

Diarrhea is the major dose-limiting toxicity of neratinib with onset typically occurring early in the course of treatment (during the first few weeks of treatment). Primary prophylactic use of antidiarrheal medication is **mandatory** for all enrolled patients in the neratinib treatment arm. Loperamide is the recommended standard therapy to treat diarrhea in this study. If alternative antidiarrheal medication is proposed, this should be discussed with the Medical Monitor and the reason documented in the source documents. Second-line antidiarrheal treatments and adjunctive therapies (i.e., octreotide [SANDOSTATIN[®]]) (or equivalent as approved by the Sponsor) are also recommended for use when appropriate.

The Investigator must review with the patient the **Patient Instructions** for the management of diarrhea and the **Patient Diary** for the patient's daily recording of investigational product during the first 2 cycles, number of stools, and use of loperamide and/or other anti-diarrheals for patients in the neratinib treatment arm. Both the patient and the Investigator must sign the patient instructions for the management of diarrhea. The Patient Instructions and Patient Diary are to be handed to the patient before leaving the site with investigational product on or before Cycle 1/Day 1, with clear instructions to contact the Investigator in the event of *de novo* onset or persistent Grade ≥ 2 diarrhea to discuss the appropriate course of treatment. The Investigator must also complete and sign the **Investigator Checklist** on or before Cycle 1/Day 1.

Documentation of any occurrences of stools or diarrhea must be as precise as possible and captured in the Patient Diary. For AE recording, documentation of "Intermittent" events of diarrhea is limited to Grade 1. If events of Grade 1 diarrhea are separated by 3 days without any diarrhea, then each event must be documented as separate AEs with corresponding start and stop dates.

The entries on the Patient Diary should be reviewed together with the patient for the first 2 cycles. If the patient has experienced diarrhea since the last visit, details of the daily number of

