stools provided on the diary help to grade the diarrhea as precisely as possible (per NCI CTCAE v.4.0). Also, the daily dose of loperamide (or other anti-diarrheals, if applicable) noted on the diary for patients in the neratinib treatment arm will be reviewed and recorded on the CRF.

Loperamide will be dispensed directly by the site on or before Cycle 1/Day 1 with neratinib. It is very important to initiate treatment with loperamide concomitantly with the first dose of neratinib to minimize occurrence and severity of diarrhea.

Prophylactic dosing instructions (Cycle 1)

- Inform patients that they will experience diarrhea while taking neratinib.
- Administer loperamide: initial dose of 4 mg (2 tablets/capsules) with the first dose of neratinib, followed by 2 mg (1 tablet/capsule) every 4 hours for the first 3 days. After the first 3 days, take loperamide 2 mg every 6 to 8 hours until the end of the first cycle of therapy regardless of whether the patient is experiencing diarrhea or not.
- For patients with persistent Grade 1 diarrhea (<4 stools per day above baseline) on loperamide, Lomotil[®] (diphenoxylate hydrochloride and atropine sulfate) 1 tablet (2.5 mg) every 6 to 8 hours may be added (or equivalent as approved by Sponsor).
- For Grade 2 diarrhea during Cycle 1 (4 to 6 stools per day above baseline, despite intensive anti-diarrheal therapy), consider adding octreotide (short-acting) 150 µg subcutaneous [SC] injection 3 times a day, or after initial dose of short-acting octreotide, if well tolerated, a single dose of octreotide LAR 20 mg by intramuscular injection (equivalent medication may be used with approval of the Sponsor).
- The sites must contact the patient by phone at 1 day, 2 days, and 3 days after the first dose of neratinib to inquire about any diarrhea.

(These phone calls are mandatory and must be recorded in the study chart together with response from the patient and action taken.)

- Instruct patients to promptly report diarrhea symptoms.
- Instruct patient to record the number of stools per day (see Patient Diary, Section 8.5) and the dose of anti-diarrheal medication taken each day (for patients in the neratinib treatment arm) for the first 2 cycles.

For new onset uncomplicated Grade 1 or Grade 2 diarrhea (Cycle 2 and beyond)

Dietetic measures

- Stop all lactose-containing products.
- Drink 8 to 10 large glasses of clear liquids per day.
- Eat frequent small meals.

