8.5 Patient Diary

The Patient Diary used for recording of investigational product intake during the first 2 cycles. The number of stools per day will also be recorded on the Patient Diary for the first 2 cycles. In addition, patients in the neratinib treatment arm will record the use of loperamide/other antidiarrheal treatment taken along with the dose of neratinib for the first 2 cycles.

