3. GENERAL ANALYSIS AND REPORTING CONVENTIONS

All study variables will be listed. Selected variables will be summarized and, when appropriate, analyzed. Data summaries will be presented by treatment group and, when appropriate, visit.

For all safety and efficacy variables, the number of patients will be provided overall and by visit, with the exception of adverse events and concomitant medications, which will not be summarized by visit.

Categorical variables will be summarized using counts and percents. Percents will be displayed to 1 place after the decimal point (XX.X), with the exception of 100%, which will be displayed without additional decimal places. Continuous variables will be summarized using number of patients, mean, median, standard deviation, minimum, and maximum.

Mean and median will be reported at 1 more significant digit than the precision of the data; standard deviation will be reported at 2 more significant digits than the precision of the data. Minimum and maximum will be reported to the same level of precision as the original observations. In general, any calculated values, such as those due to unit conversion, will be rounded to the same number of decimal places as the original data. P-values will be reported to 3 decimal places, with values less than 0.001 displayed as '<0.001.'

In general, the baseline value will be considered the last measurement observed prior to taking the first dose of study treatment.

Data will be listed by treatment and patient. In general, listings will be sorted in the order that columns are displayed, starting with the first column on the left (treatment).

SAS statistical software, version 9.1 or later, will be used for all analyses.

If departures from these general conventions are present in the specific evaluations section of this SAP, then those conventions will take precedence over these general conventions.

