12. LIST OF PLANNED TABLES

Grouping	Title
Disposition	Summary of Subject Disposition
	Summary of Protocol Deviations
Demography	Summary of Demographics and Baseline Characteristics
Medical History	Summary of Medical History
Cancer History	Summary of Prior Cancer History and Therapies
	Summary of Baseline Breast Cancer Disease Burden
	Summary of Prior Anticancer Medications
	Summary of Prior Anticancer Radiotherapy
	Summary of Prior Anticancer Surgical Therapy
	Summary of Biomarkers
Concomitant Medications	Summary of Concomitant Medications
	Summary of Non-Pharmacologic Anti-Diarrheal Treatments
Study Medication	Summary of test article exposure
	Summary of test article dose reduction
	Summary of test article dose hold
Efficacy	Summary of Progression-Free Survival
	Summary of Censoring in Progression-Free Survival
	Summary of Objective Response Rate
	Summary of Duration of Response
	Summary of Censoring in Duration of Response
	Summary of Clinical Benefit Rate
	Summary of Overall Survival
Health Outcomes	Summary of Censoring in Overall Survival
	Summary of EORTC QLQ C30 BR23 Observed Results
	Summary of EORTC QLQ C30 BR23 Change from baseline
	Summary of EORTC QLQ C30 BR23 Mixed Model Between Treatment Comparison
	Summary of EQ-5D Observed Results
	Summary of EQ-5D Change from baseline

Grouping	Title
	Summary of EQ-5D Mixed Model Between Treatment Comparison
	Summary of EQ-VAS Observed Results
	Summary of EQ- VAS Change from baseline
	Summary of EQ- VAS Mixed Model Between Treatment Comparison
Safety	Frequency Table of Treatment Emergent Adverse Events by Body System and Preferred Term
	Frequency Table of Serious Adverse Events by Body System and Preferred Term
	Frequency Table of Treatment Emergent Adverse Events Leading to Study Discontinuation by Body System and Preferred Term
	Frequency Table of Treatment Emergent Adverse Events Leading to Study Drug Reduction by Body System and Preferred Term
	Frequency Table of Treatment Emergent Adverse Events Leading to Study Drug Hold by Body System and Preferred Term
	Frequency Table of Treatment Emergent Adverse Events by Body System, Preferred Term and Relationship to Study Medication
	Frequency Table of Treatment Emergent Adverse Events by Body System, Preferred Term and Severity
	Frequency Table of Treatment Emergent Adverse Events by Body System and Preferred Term (Toxicity Grade 3 or Higher)
	Summary of Death
Diarrhea	Summary of Time to First Diarrhea Treatment Emergent Adverse Event

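### SAP 9.3 compares antidiarrheal treatment between arms, but diary recording and mandatory prophylaxis apply only to the neratinib arm, and the SAP neither names a common data source nor separates prophylaxis from treatment

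*SAP*

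**What the plan says.** SAP 9.3 sets the comparison: "Therapies used to treat diarrhea will also be summarized using descriptive statistics and compared between treatment groups". The SAP's list of planned tables adds a summary of antidiarrheal medications and, for onset, a "Summary of Time to First Diarrhea Treatment Emergent Adverse Event", with a further version by severity. SAP 3 gives the display rule: "Data summaries will be presented by treatment group and, when appropriate, visit".

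The protocol treats the arms differently in three respects.

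- **Required use.** Protocol 7.1.1: "Primary prophylactic use of antidiarrheal medication is mandatory for all enrolled patients in the neratinib treatment arm".
- **Recording.** Protocol 8.5 says that, for the first two cycles, "patients in the neratinib treatment arm will record the use of loperamide/other antidiarrheal treatment taken". Protocol 7.1.1 says that the daily dose "noted on the diary for patients in the neratinib treatment arm will be reviewed and recorded on the CRF".
- **Early contact.** Protocol 7.1.1: "The sites must contact the patient by phone at 1 day, 2 days, and 3 days after the first dose of neratinib". No equivalent is described after the first lapatinib dose.

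Two other places describe the diary differently. Protocol 8.2 and SAP 9.3 both say that it captures antidiarrheal use, with no restriction by arm.

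**The concern.** A between-arm comparison needs the same quantity measured in the same way in both arms. Here one arm has a daily diary record of antidiarrheals carried to the CRF. The other has only what is captured as concomitant medication. One arm also takes loperamide through Cycle 1 by rule, with or without diarrhea. If the table pools all antidiarrheal records, a difference between arms could arise with no difference in diarrhea at all.

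The stake is a safety comparison and no primary endpoint is affected. It is not a marginal one, though: Protocol 7.1.1 calls diarrhea neratinib's major dose-limiting toxicity, safety is a secondary objective compared between groups, and the trial is open-label. The conflict over the diary adds a practical risk. A programmer working from SAP 9.3 could read the absence of lapatinib-arm diary entries as absence of use.

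**Working it through.** No formula or stated figure is in question. The check is to set the collection rules for the two arms side by side.

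| Item | Neratinib arm | Lapatinib arm | Source |
|---|---|---|---|
| Antidiarrheal prophylaxis | Mandatory from the first dose through Cycle 1 | Only to be considered, after diarrhea of a given grade | Protocol 7.1.1; Appendix 2, Table A2.9 |
| Antidiarrheal entries in diary, Cycles 1-2 | Yes | Not required | Protocol 7.1.1, 8.5 |
| Daily dose moved from diary to CRF | Yes | Not stated | Protocol 7.1.1 |
| Calls about diarrhea 1, 2 and 3 days after first dose | Yes | Not stated | Protocol 7.1.1 |
| Stool counts in diary, Cycles 1-2 | Yes | Yes | Protocol 8.5 |
| Concomitant medications with dates, dose, indication | Yes | Yes | Protocol 7 |
| AE reporting; Day 8 and Day 15 visits | Yes | Yes | Protocol 4.1, Appendix 1 |

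**Extent of the unequal recording.** 2 cycles x 21 days = 42 diary days. With 600 patients randomized 1:1, 600 / 2 = about 300 per arm. Controls keep the same diary for those 42 days and lack only its antidiarrheal entries.

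**What remains for the lapatinib arm.** Protocol 7 has patients asked at each visit what they are currently taking. Visits fall on Days 1, 8 and 15 of Cycle 1 and then on Day 1 of each cycle. The nominal gap is therefore 7 days in Cycle 1 and 21 days from Cycle 2. A short course taken between visits is easier to miss in this arm than in one with daily entries.

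**What the SAP does about it.** SAP 9.3 does not say whether the comparison draws on the diary-derived CRF data or on concomitant medications. SAP 6.3 defines concomitant medications by their own CRF but is not tied to the comparison in 9.3. Neither section has a rule for separating prophylactic from therapeutic use.

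**Onset.** Stool diary, AE reporting and early visits are common to both arms, which leaves the three calls as the only one-armed element. An episode on Day 2 that is found from the diary at the Day 8 visit can still be dated to Day 2. The calls therefore matter only for episodes that diary, visit and patient report would all miss. The documents give nothing from which to estimate that number.

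**The case against.** The strongest reply is that the comparison is already feasible. SAP 9.3 speaks of treatment for diarrhea and not of all antidiarrheal use, and Protocol 7 collects the indication for every medication in both arms. On this view only a sentence is missing. Much of this stands: a common source exists and can support the split. But the SAP does not name it, the planned antidiarrheal table is not limited to therapeutic use, and the protocol sets up a richer one-armed source for the same information.

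Stronger readings are tempting and should be resisted.

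- A reader might infer that antidiarrheal use is fixed near 100% against a lower figure. That could follow only if prophylaxis is pooled with treatment, and the SAP leaves this open.
- A reader might infer that early diarrhea is solicited in one arm only. Apart from the calls, the means of detection listed above are common to both arms.
- A reader might infer that the SAP tests onset between arms. It lists a by-arm summary and names no test.
- The 2-day median onset in Protocol 2.2.3.4 comes from an earlier study for which no mandatory prophylaxis is mentioned, so it cannot be carried over to this trial.

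It can also be said that the extra capture works against the experimental arm. That is probably so, but a bias in a known direction still distorts the comparison.

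**Conclusion.** The concern holds for antidiarrheal use. A stated one-arm recording rule and a one-arm prophylaxis requirement feed a stated between-arm comparison, and the SAP has no rule to handle either. The likely direction is to make use look higher in the neratinib arm relative to control. The size cannot be derived from the documents.

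For onset, the finding is limited to three calls of unknown effect. Any influence of prophylaxis on onset belongs to the assigned regimen and is not an ascertainment error.

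The conclusion assumes that sites follow Protocol 7.1.1 and 8.5 rather than the unrestricted description in Protocol 8.2. If lapatinib patients do record antidiarrheals and those entries reach the CRF in the same way, the recording gap closes, but the mixing of prophylaxis with treatment remains. The proposed split also relies on sites recording the indication accurately. This is a worthwhile, low-cost improvement to a safety output and does not threaten the primary analyses.

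**What to change.** 1. **Protocol 7.1.1 and 8.5.** Have both arms record antidiarrheal use in the diary they already keep, and transcribe it to the CRF in the same way. Reconcile Protocol 8.2 and SAP 9.3 with these sections so that all four describe the same data. Cost: one diary entry and its transcription for the control arm.
2. **SAP 9.3.** Tabulate prophylactic and therapeutic use separately by recorded indication, and say where loperamide continued after a resolved episode is counted. Compare only therapeutic use, from a source collected identically in both arms. If the diary can no longer be changed, name the concomitant-medication CRF as that source and show neratinib diary doses as single-arm description. Cost: SAP wording and programming on data already collected.
3. **Time-to-first-diarrhea tables.** State beside them, as a limitation, that the Day 1-3 calls were made in one arm only. Cost: a footnote.

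Making raw stool counts the main basis for comparing diarrhea is not recommended. Neither document says that the counts reach the CRF, and the SAP lists no stool-count output. The diarrhea grades in Appendix 2 are relative to baseline and also use incontinence, hospitalization and self-care. Investigator-graded treatment-emergent events should remain the basis.

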9.4. Clinical Laboratory Evaluation

Blood samples for clinical chemistry and hematology will be collected during screening, before study drug administration, on day 1 of each treatment cycle and at the treatment discontinuation visit. Samples for pregnancy test and urinalysis will be collected at screening and before study drug administration.

Laboratory data will be summarized in tables using descriptive statistics for baseline and each cycle/visit. Descriptive statistics will be calculated on both the actual score and the change from baseline score. Additionally, clinically significant abnormalities in laboratory results will be summarized for the post-baseline cycles/visits using frequencies and percentages. Shifts in normal/abnormal status between baseline and subsequent visits will be summarized as well.

The institutional laboratory will analyze all hematology, routine blood chemistry, and urine samples collected.

9.5. Vital Signs, Physical Findings, and Other Observations Related to Safety

9.5.1. Vital Signs

Vital signs, including systolic and diastolic blood pressure, pulse, and body temperature, as well as weight will be collected during screening and on days 1, 8 and 15 of cycle 1 and on day 1 of the following cycles. Height will be collected at screening.

Summary tables will include descriptive statistics (number of patients, mean, std, median, min, and max) for baseline and each cycle/visit. Descriptive statistics will be calculated on both the actual score and the change from baseline score. Supplemental data will not be included in this summary; therefore the latest assessment in the cycle/visit window will be used for the evaluation.

A second summary will focus on the individual patient measures with the intent of identifying post-baseline abnormalities defined as clinically significant.

